The final 100 participants in the UPWARD sample of 600 individuals will participate in an abbreviated version of the UPWARD procedures. These 100 women will be recruited via the same platform of BabyCenter, screened and enrolled based on the same entry criteria, and similarly randomized to the MMB intervention or Usual Care. However, the only differences will be that these final participants in this group of 100 who are randomized to the treatment group will not receive the coaching that is typically involved in the MMB intervention. This will further investigate our research aims to assess the extent to which this modified version of MMB is still an effective means of preventing depressive relapse in a perinatal population. Moreover, these final 100 participants will not receive any follow-up clinical interviews or relapse determination calls after the initial screening and baseline calls. Participants will be randomized after the baseline call, either through a phone conversation or via email. They will instead be prospectively followed through 3 months postpartum via the same battery and schedule of self-report questionnaires given to the other UPWARD participants through this timepoint. If any participant endorses items 3, 4, or 5 on the C-SSRS via these self-report questionnaires, the same suicidality safety protocol will be triggered as outlined below. The information about the delivery and newborn outcomes that would typically be collected during the 3 months postpartum interview will now be administered as a self-report survey with the rest of the questionnaires for this timepoint.

Table 2. UPWARD Extension Measurement Schedule

UPWARD Study	Baseline	M1	W6	M2	Post-Intervention	M3	M4	M5	3T	M6	M7	M8	3PP
MINI full	x												
MINI mood	x				x				x				x
MADRS	x				x				x				x
EPDS	x	x	x	x		x	x	x	x	x	x	x	x
PHQ-9*	x	x	x	x		x	x	x	x	x	x	x	x
CS-S**	x												
CGI	x				x				x				x
PGI	x	x	x	x		x	x	x	x	x	x	x	x
GAD-7	x	x	x	x		x	x	x	x	x	x	x	x
PSS-10	x					x			x				x
WHODAS 2.0	x					x			x				x
CSQ-8 (UC)	x					x							
CSQ-8 (MMB)						x							
CTQ	x												
PROMIS	x												
FFMQ	x		x			x							
RRS	x		x			x							
SCS	x		x			x							
SSQ-SF	x					x							x
RSQ-MEP	x												
LEL	x												
LEIDS-R	x		x			x							
EQ	x		x			x							
CSI	x												
AToM	x					x			x				x
PSA	x		x			x			x				
PSQI	x					x							x
Positive Mood Diary	x		x			x							

DPES Joy Subscale	x		x		x					x
CERTS Unresolution Subscale	x									

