5	Facing Difficulties	Increasing use of mindful attention at the first step in responding effectively to difficulties, including difficult internal experience such as sadness; decreasing judgmental thoughts and avoidant responses to difficulties.
6	Thoughts Are Not Facts	Decreasing affective reactivity to thoughts previously associated with depression; learning to “de-center” from difficult thoughts, recognizing one’s personal patterns of recurring thoughts,
7	Building Your Plan of Action	Identifying unique ‘signatures’ of mood worsening; identifying activities that improve or deteriorate mood; developing action

		plans to implement during periods of high risk; using mindfulness practice explicitly to guide action plan steps.
8	Supporting Your Practice in the World	Emphasizing the importance of regular self-care routines, identifying 'your daily routine of mindfulness practice'; reinforcing links between mindfulness practices, wellbeing and maintenance

MMB for Moms may be a promising intervention for pregnant women with suicidal ideation, as it delivers digitally both the content and structure of in-person MBCT. The standard MMB for Moms program will be implemented for participants in UPWARD Supplemental Arm 2; however, measurement expansion for Supplemental Aim 2 will probe participant responses to the content and the potential need for additional information specific to suicidal ideation and behaviors.

Usual Care (UC). Usual care will not be constrained for any study participants, including those randomized to MMB. The study will not constrain or influence women's decisions about maintenance or discontinuation of AD for all participants. Usual care will be augmented in two ways. First, we will provide ongoing study assessments and the provision of feedback to participants based on their responses to the PHQ-9, EPDS, and clinical interviews (e.g., "Your answers seem to suggest that you are having significant symptoms of depression. We recommend that you talk with your community care provider about whether treatment or modification of treatment might help"). Usual care also will be augmented by ongoing availability of study physicians with perinatal psychiatric expertise in response to queries from community providers regarding changes or reintroduction of pharmacologic treatment during pregnancy or the postpartum period for study participants.

Prospective Follow-up and Community Outreach

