In UPWARD, UPWARD Extension and UPWARD-S, if suicidality is endorsed with a score of greater than 1 on EPDS item #10 or PHQ-9 item #9 or on any of the self-report questionnaires (such as the SITBI or CCM), subjects will be prompted to complete the CS-S to assess risk of suicidality. Study subjects will also be given the national suicide [contact]) and informed that answers to online questionnaires are not monitored in real time. A positive score on questions 3, 4, or 5 on the CS-S, indicating intention or plan for suicidality, will prompt a safety call by study physicians. Suicidality expressed during the course of clinical or qualitative interviews, either through discussion, endorsement of the suicidality item on the MINI mood module, endorsement of items 3, 4, or 5 on the suicidality module of the MINI, or via scoring >2 on the MADRS item 10, will prompt study staff to complete the CS-S with the participant. A positive score on items 3, 4, or 5 of the CS-S administered by staff will also prompt a safety call by study physicians. In addition, subjects will be told by study staff to call their community providers and go to their nearest emergency room. Endorsement of items 3-5 on the CS-S prompting a physician safety call has been the threshold used in previous studies at the collaborating site (University of Colorado Boulder). As this is a community-based study with collaboration from community physicians, these providers dictate treatment. We will notify community providers directly via phone or fax within 24 hours from report of positive scores on CS-S items 3-5.

VI. BIOSTATISTICAL ANALYSIS

Preliminary Analyses: Differences between the MMB and UC in demographic characteristics and depression related characteristics (e.g., symptom severity, comorbidity) will be assessed using Chi-square test for binary variables, Cochran Mantel Haenszel tests for categorical variables, and t-tests for continuous variables. Variables that show significant group differences and predict outcome will be entered in analyses as covariates; AD exposure will be included as a covariate. All participants will be considered evaluable for analysis (intent-to-treat sample). Significance levels will be evaluated at $p < .05$, and effect sizes reported.

Analysis for Specific Aim #1: To test the relative risk for depressive relapse and reduction of symptom burden between women randomized to digital MMB or UC.

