For the analysis of rates of relapse, we will examine time to relapse as rated by the MINI during pregnancy and across the 6-month postpartum follow up using survival analysis. Survival rates will be compared using Cox proportional hazard regression and illustrated in Kaplan-Meier curves (Collett, 1994). However, time to attrition is a competing risk that can be related to time to relapse. We will adopt the subdistribution hazard model (SHM) developed by Fine and Gray to account for the possible non-independence of the censoring mechanism.²⁵

For the continuous outcomes, we will use Hierarchical Linear Models (HLM) as our primary analytic model, which will compare change over time between groups on depressive symptom burden using the PHQ-9. HLM is flexible with respect to the nature of change over time (i.e., linear, piecewise linear, loglinear, etc.), and will accommodate the within subject correlation through the inclusion of random effects at the patient-level, accounting for the patient-to-patient deviations. Pattern-mixture models²⁶ will be used to assess whether important estimates (i.e., intervention effects) are dependent on missing data and to provide overall estimates of effects by averaging over the various missing-data patterns.

Analysis for Specific Aim #2: To explore the specific benefit of MMB relative to AD discontinuation and questions regarding personalization that are of strong interest to pregnant women and their healthcare providers.

H2a: Comparison of MMB to UC among women who discontinue AD: Our analysis will be the same as H1 with both the time-to relapse and continuous outcome models. We predict that rates of relapse and symptom burden among women randomized to MMB who discontinue AD will be significantly superior to those randomized to UC who discontinue AD.

H2b: Treatment Selection Algorithm: We predict that the use of a treatment selection algorithm will differentiate two profiles of women based on pre-treatment characteristics (those who are optimally suited to discontinue AD and engage MMB to minimize their risk of relapse, and those who should continue AD to minimize risk of relapse) and that women who are randomized to the algorithm indicated approach will have significantly lower risk of relapse and symptom burden than women who are randomized to their algorithm contraindicated approach.

Analysis for Specific Aim #3: To test the extent to which digital MMB engages putative targets.

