If a participant scores greater than or equal to 15 on the PHQ-9 or greater than or equal to 12 on the EPDS, the online data collection and management system (REDCap) will automatically provide participants with contact information for national mental health crisis resources and for the research study team. Study investigators will be notified immediately via an algorithm programmed into REDCap. In the UPWARD parent trial and UPWARD-S Arms 1a and 2, study staff at MGH will initiate a clinical response by phone call to assess clinical status and suicidality as soon as possible within 24 business hours of report. The score of 15 is suggested as the threshold for moderate depression.³⁹ Additionally, we will monitor specifically responses to the suicide item (#9) on the PHQ-9: 'Thoughts that you would be better off dead or hurting yourself in some way.' and the suicide item (#10) on the EPDS: 'The thought of harming myself has occurred to me' for all study participants. If a participant endorses either of these items with a score of 1 or greater, REDCap will automatically route participants to fill out the Columbia Suicide Severity Rating Scale (CS-S) and provide participants with contact information for national mental health crisis resources and for the research study team. Study investigators and staff will be automatically notified by the REDCap system for a positive score on questions 3-5 of the CS-S in order to provide outreach as soon as possible within 24 hours and assessment of the patient by a study doctor. In UPWARD-S, endorsement of current suicidal ideation on the SITBI or CCM item (#11) will also automatically route participants to fill out the CS-S. Any endorsement of items 1-5 of the CS-S will prompt administration of the full CS-S to capture duration and intensity of suicidal ideation and/or behaviors. Furthermore, any participant who misses a scheduled assessment point will be contacted immediately by study staff. Study staff will continue to try to reach participants until a participant indicates that they no longer wish to be contacted or the participant has reached six months postpartum by their estimated date of delivery, whichever comes first. Throughout the study, all participants also will be encouraged to contact the study staff at the first sign of increased depression.

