We anticipate that the additional 12-months postpartum timepoint (UPWARD-Baby) will not present any additional risk for participants compared to that of the parent study. Because we are asking the PHQ-8 at this timepoint instead of the PHQ-9 (which is what is asked throughout the parent study), we will not learn about suicidal ideation and therefore a safety plan for SI is not needed.

VIII. POTENTIAL BENEFITS

Participants may benefit from ongoing clinical monitoring of depressive symptoms and, in all arms except UPWARD Extension, provision of feedback. In addition, participants assigned to the MMB condition may experience an increase in knowledge about depression and how to decrease future risk for relapse. All participants enrolled in the study will have any benefits afforded by the assessment protocol with respect to the possible early identification of depressive symptom exacerbation and information about accessing national mental health services and potential consultation to their community prescriber. Since contact with the study team will occur at multiple time points, subjects will have the opportunity to easily access experts in the area of depression and pregnancy.

Lastly, subjects will be compensated for their participation. Participants in the parent UPWARD Study will be compensated \$175 for their participation in the study. Participants in UPWARD Extension will be compensated a total of \$140 for their participation in the study. Participants in UPWARD Supplement Arms 1a and 2 will be compensated \$200 for their participation in the study (\$25 more than parent UPWARD study to compensate for participation in qualitative interviews and additional self-report questionnaires). Providers that participate in UPWARD Supplement Arm 1b will be compensated \$75 for their participation in the qualitative interview.

Study physicians with expertise in perinatal psychiatry will be available as a resource to community providers for advice and management of participants' clinical care. If questions arise regarding changes or reintroduction of pharmacologic treatment during pregnancy or the postpartum period, study physicians can provide consultations to these providers, thus spreading clinical knowledge and equipping providers with the tools to provide evidence-driven care.

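### The 100-woman Extension delivers MMB without coaching, but Section VI contains no analysis that could show whether that version works

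*Combined protocol and SAP*

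**What the plan says.** Section V (UPWARD Extension) states: "The final 100 participants in the UPWARD sample of 600 individuals will participate in an abbreviated version of the UPWARD procedures". They are randomised to MMB or UC like the others, but those "who are randomized to the treatment group will not receive the coaching that is typically involved in the MMB intervention". The MMB Treatment Protocol text confirms this and describes coaching as manual-based over a 12-week intervention period. The Extension section also removes clinical interviews after baseline and relapse determination calls in both arms, and ends follow-up at 3 months postpartum instead of 6. It gives the cohort a purpose: to assess "the extent to which this modified version of MMB is still an effective means of preventing depressive relapse".

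Section VI does not mention the Extension. Preliminary Analyses says: "All participants will be considered evaluable for analysis (intent-to-treat sample". The Aim 1 model is to "compare change over time between groups on depressive symptom burden using the PHQ-9". Power is quoted for 300 per group. No cohort term, interaction, separate Extension estimate or Extension power is given.

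The documents disagree on what else differs for these women:

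- The Extension section calls the loss of coaching the only difference, then adds the loss of interviews and relapse determination calls.
- The Usual Care text in Section V says "Usual care will be augmented in two ways". The first way is ongoing assessment with feedback on scores. Section VII repeats this. Neither exempts the Extension.
- Section VIII lists as a benefit, "in all arms except UPWARD Extension, provision of feedback".
- Section VII, on PHQ-9 scores of 15 or more or EPDS scores of 12 or more, says: "In the UPWARD parent trial and UPWARD-S Arms 1a and 2, study staff at MGH will initiate a clinical response by phone call". The Extension is not listed.

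**The concern.** One sixth of the MMB arm receives a different intervention, under different study contact, and the analysis plan does not separate it. Two readings of the result are then at risk. The pooled PHQ-9 effect could be reported as the effect of the coached programme when it is an average over two versions. And a positive pooled result could be taken as support for uncoached MMB, which about 50 women receive and which matters for scaling up a digital programme.

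The stated purpose of the Extension concerns relapse, while the Aim 1 relapse outcome is MINI-rated and the Extension text removes the interviews and calls at which the MINI would be given. A direct comparison of coached with uncoached women would not help either. It is not randomised, and it coincides with enrolment period and with the change in study contact.

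**Working it through.** **Inputs.** From the documents: 600 women, 100 of them in the Extension; 1:1 allocation; 30% attrition; two-sided alpha 0.05; within-woman correlation 0.5; effect size 0.25 (Section VI, power for Aim 1). Assumed: an even Extension split (50 v 50), the same 30% attrition there, and m = 6 repeated measures, because m is not stated.

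**Formula.** For a mean of m measures, f = (1 + (m − 1) × 0.5)/m, SE = sqrt(2f/n), and power = Φ(d/SE − 1.96). At m = 6, f = 3.5/6 = 0.583.

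**1. The plan's own figure.** With n = 175 per arm, SE = sqrt(1.167/175) = 0.0816 and 0.25/0.0816 = 3.06, so power is 86.5%, as stated. Effects of 0.30, 0.35 and 0.40 give 95.7%, 99.0% and 99.8%, also as stated. The match is not unique:

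- m = 5 to 8 gives 85.5% to 87.7% at d = 0.25.
- n = 300 with a single measure and no attrition gives the same four values.
- n = 210 with m = 3 gives 88.1% at d = 0.25.

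**2. Which sample was powered.** The plan starts from 300 per group, takes off 30% and arrives at 175. But 300 × 0.7 = 210, and 175 = 250 × 0.7. The figure 250 per arm is the trial without the Extension.

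**3. The pooled effect.** With each woman counting equally, pooled d = (250 × 0.25 + 50 × d_u)/300, where d_u is the effect of uncoached MMB. Power uses n = 210 and m = 6 (SE = 0.0745).

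| Uncoached effect d_u | Pooled d | Power |
|---|---|---|
| 0.25 (same) | 0.250 | 91.8% |
| 0.125 (half) | 0.229 | 86.8% |
| 0 (none) | 0.208 | 79.8% |

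The pooled test therefore succeeds about four times in five even when the uncoached version does nothing.

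**4. The Extension alone.** With 35 v 35 retained, SE = sqrt(1.167/35) = 0.183.

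- Power at d = 0.25 is 27.7% (27.1% at m = 5, 29.5% at m = 12).
- With no attrition (50 v 50, m = 6) it is 37.3%.
- The 95% CI half-width is 1.96 × 0.183 = 0.36 SD.
- The effect detectable with 80% power is (1.96 + 0.842) × 0.183 = 0.51.
- On a single endpoint (m = 1), power is only about 18% with 35 per arm and 24% with 50.

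**5. Cohort-by-arm term.** SE = sqrt(0.0816² + 0.183²) = 0.20. Power for a difference of 0.25 between the two versions is Φ(1.25 − 1.96) = 24%.

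**6. Relapse in the Extension.** The Section V text and the follow-up section allow only screening and baseline calls. Table 2 (UPWARD Extension Measurement Schedule) still lists MINI mood, MADRS and CGI at post-intervention, third trimester and 3 months postpartum. If the text governs, the outcome named in the Extension's purpose is not assessed after baseline.

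**The case against.** Several points on the other side stand.

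- **Pooling is inferred.** No sentence puts the Extension into the PHQ-9 model. The sample of 600, the all-participant ITT set and 300 per group point that way, while 175 per arm fits the 500 parent-procedure women. A reader might infer that the Extension was meant to be excluded. The documents do not settle this either: the same sentence begins from 300 per group, and 175 may be a leftover.
- **The pooled contrast is not biased for what it estimates.** Women are randomised within the Extension. A reader might infer that the Aim 1 comparison is invalid, but it remains a valid ITT test of a mixture. The dilution is modest, and actual model weights may differ because Extension follow-up ends earlier.
- **Restricting to about 500 women is a trade-off.** If uncoached MMB has half the effect, pooled power (86.8%) is no worse than power in the 500 (86.5%), and the restriction sets aside randomised women.
- **Study contact is not all removed.** A reader might infer that Extension women get no staff calls. Screening and baseline calls, the suicidality safety protocol with its physician call, and contact after a missed assessment remain, and the physician consult line is not withdrawn. The Extension section also discloses the loss of relapse determination calls, which are triggered at the same PHQ-9 and EPDS thresholds as the Section VII phone response.
- **A changed comparator is not established.** The statement that feedback is withheld rests on one clause in Section VIII, against Section V (Usual Care) and Section VII. That is a conflict, not a settled fact.

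None of this supplies an analysis of uncoached MMB.

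**Conclusion.** The concern holds in this form: the plan gives the Extension a stated purpose that no planned analysis serves, and it does not say how the Extension enters the PHQ-9 comparison. If all 600 are pooled, the result describes a roughly 5:1 mix of coached and uncoached MMB. With a coached effect of 0.25, the pooled effect lies between 0.208 (no uncoached effect) and 0.250 (equal effect). A positive pooled result is no evidence for the uncoached version, since power is about 80% when that version does nothing. The Extension alone can give only an imprecise estimate, within about 0.36 SD either way.

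These sizes assume six measures, correlation 0.5, 30% attrition in both cohorts, an even Extension split and equal weight per woman. Varying the number of measures does not change the conclusion. The silence of Section VI is certain; pooling is a strong inference. Validity of the ITT contrast is not in question, so this should be corrected but is not fatal.

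**What to change.** - **Model.** In Section VI, add a cohort main effect (parent or Extension) and a cohort-by-arm term to the all-600 PHQ-9 model. Report the MMB-minus-UC difference separately for the parent-procedure women (about 500) and for the Extension, each with a 95% CI, and label the Extension estimate exploratory.
- **Main estimate.** State before analysis which sample gives the main PHQ-9 estimate, and correct the mismatch between 300 per group with 30% attrition and 175 per arm. If the 500 are chosen, 175 per arm retains the stated 86.5% power (m = 6). If all 600 are chosen, describe the result as an average over both versions.
- **Claim.** In Section V (UPWARD Extension), replace the statement about relapse prevention with an exploratory PHQ-9 estimate for uncoached MMB. State that coached-versus-uncoached differences are not randomised and are confounded with enrolment period and study contact.
- **Consistency.** Reconcile the Extension section's account of the differences, the Usual Care text, the feedback and high-score phone response in Section VII, and the exception in Section VIII. Also reconcile the Extension text with its Table 2. Which version applies is for the sponsor to state.

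The cost is wording, two model terms and slightly more reporting. The interaction will be imprecise, with about 24% power for a difference of 0.25, so it should be read from its interval and a non-significant result should not be taken as equivalence of the two versions.
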